# 9.6 Withdrawal of Individual Subjects

A subject will be withdrawn from the study if the subject meets any of the following criteria:

- lost to follow-up
- requests to be withdrawn from the study
- has been found to be ineligible for participation in the study
- the Investigator (or subinvestigator) judges continuation of the study to be difficult due to AEs (eg, hypersensitivity reactions)
- is pregnant
- requires tracheostomy
- requires permanent assisted mechanical ventilation (≥ 23 hours/day)
- the Investigator (or subinvestigator) judges continuation of the study to be inappropriate due to exacerbation of the primary disease
- significant hepatic abnormalities
  - ALT or AST > 8 x ULN OR
  - Persistent ALT or AST > 5 x ULN OR
  - ALT or AST > 3 x ULN with concomitant bilirubin > 2 x ULN
  - Symptoms consistent with liver dysfunction (eg, fatigue, nausea, vomiting, abdominal pain/tenderness, fever, rash, eosinophilia > 5%) with concomitant ALT or AST greater than 3 times the ULN
  - Note: subjects meeting these criteria do not require withdrawal if alternative etiology is identified on discussion with the Study Medical Monitor
- Noncompliance (ie, misses more than 20% of doses in 2 consecutive dosing cycles, after consultation with Mitsubishi Tanabe Pharma Development America [MTDA] or designee).
- a surgery on the spine, such as surgery for cervical spondylosis or herniated disk is performed
- initiates therapy de novo with riluzole or other excluded medication during the treatment period

If a subject is withdrawn prematurely from the study, the date the subject is withdrawn from the study and the reason for withdrawal will be recorded in the electronic case report form (eCRF).

In the event that a subject drops out of the study at any time, the reason for discontinuation must be fully documented in the source documents and the eCRF. The investigator site personnel will document the AEs and any other assessments in the source documents and will make every effort to complete all required ET assessments. Study sites must follow-up with phone calls at Weeks 24, 36, and 48.

Subjects who are withdrawn due to liver dysfunction should be followed until resolution and assessed for alternative etiologies.

Subjects who are withdrawn from the study following enrollment may not re-enter the study.

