#### 14.3 Treatment Compliance

The prescribed dosage, timing, and mode of administration of study medication may not be changed except for switching from oral to PEG/RIG tube dosing as the subject's disease progresses. An electronic diary (e-diary) will be used to collect data surrounding subject compliance with dosing and will provide reminder notifications to subjects in order to aid in compliance. Subjects will be asked questions regarding compliance; any departures from the intended regimen, including if the subject has switched from oral to PEG/RIG tube dosing along with the switch date must be recorded in the eCRF.

Study drug accountability and treatment compliance will be documented throughout the study period using study medication dispensing and return record logs.

Subjects will be asked to return all unused medication including empty and partially used medication. Study medication dispensed at the previous visit will be collected by the site and compliance will be assessed by counting the returned study medication bottles. Any doses missed by the patient in each cycle must be recorded in the source and eCRF by site staff.

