The ALSAQ is a patient self-report health status PRO (Patient Reported Outcome). The ALSAQ is specifically used to measure the subjective well-being of patients with ALS.

There are 40 items in the long form ALSAQ-40, with 5 discrete scales:

- Physical mobility (10 items)
- Activities of daily living and independence (10 items)
- Eating and drinking (3 items)
- Communication (7 items)
- Emotional reactions (10 items)

Patients are asked to think about the difficulties they may have experienced during the last two weeks (e.g. I have found it difficult to feed myself). Patients are asked to indicate the frequency of each event by selecting one of 5 options (Likert scale):

never/rarely/sometimes/often/always or cannot do at all.

The Investigator (or sub-investigator) will evaluate subjects using the ALSAQ40 and rater scores will be collected at the time points described in Table 1. The evaluation results, together with the dates of evaluation, will be recorded in the eCRF. The ALSAQ-40 total score will be derived as the sum of 40 items.

8.4.2.4. Time to death, tracheostomy, or permanent assisted mechanical ventilation:

On Day 1 of study drug treatment through EOT/ET, the Investigator (or subinvestigator) will investigate the presence or absence of the following events:

- Death
- Tracheostomy
- Permanent assisted mechanical ventilation (≥ 23 hours/day)

If any of the events are present, the following will be recorded in the eCRF; the date of the

event and EOS date will be investigated. When a subject discontinues the study, study sites must follow-up with phone calls at the time points described in Table 1. The evaluation results, together with the dates of the evaluation, will be recorded in the eCRF.

The time to first occurrence of death, tracheostomy, or permanent assisted mechanical ventilation (defined on EMA Guideline on clinical investigation of medicinal products for the treatment of amyotrophic lateral sclerosis, 1 November 2015) will be derived as follow:

- In case the event mentioned above is observed any time up to the last observed visit date when week 48 data base is locked, then the time variable for each subjects will be calculated as:
 - The date of the event - Randomization date +1

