8.4.2.8. King's ALS Clinical Stage Derived from ALSFRS-R Score and Death Event

The King's ALS Clinical Staging System describes functional progression of ALS in terms of magnitude of disease involvement of different CNS regions (bulbar, upper limb, lower limb, need for gastrostomy and need for tracheostomy); according to its developers, the system was designed to inform patient-care decision making, resource allocation, research classifications, and clinical trial design11. Stages 1, 2, and 3 refer to the number of CNS regions (bulbar, upper limb, lower limb) involved at assessment, as described in Table 4 below. Stage 4A is defined solely by impairment of swallowing sufficient to require gastrostomy, and Stage 4B is defined solely by respiratory involvement sufficient to require ventilatory support. Functional involvement of three CNS regions is not a prerequisite to Stage 4A or 4B.

² Refer to Appendix I of the protocol.

Statistical Analysis Plan
Protocol No. MT-1186-A02

Mitsubishi Tanabe Pharma America, Inc.

While the King's ALS Clinical Staging System was designed initially for use as an assessment tool to be used in clinic, Balendra and colleagues¹² developed a method for estimating King's ALS Clinical Stages based on responses to ALSFRS-R items Q1 (speech), Q2 (salivation), Q3 (swallowing), Q4 (handwriting), Q5A/Q5B (self-feeding), Q8 (walking), Q10 (dyspnea), and Q12 (respiratory insufficiency)¹². The algorithm for mapping from responses to these items to King's Stage is also described in Table 4.

Table 4 : King's ALS Clinical Staging System

King's		Item Mapping
Stage	Definition	
1	Functional involvement of 1 CNS region	Bulbar involvement -- Score ≤ 3 on Q1, Q2, or Q3
2	Functional involvement of 2 CNS regions	Upper limb involvement -- Score ≤ 3 on Q4 or Q5A
3	Functional involvement of 3 CNS regions	Lower limb involvement -- Score ≤ 3 on Q8
4A	Need for gastrostomy	If Q5B is answered, rather than Q5A
4B	Need for non-invasive ventilation	Score of 0 on Q10 or score ≤ 3 on Q12
5	Death	

CNS: Central nervous system regions are bulbar, upper limb, and lower limb

Statistical Analysis Plan
Protocol No. MT-1186-A02

Mitsubishi Tanabe Pharma America, Inc.

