Since the MT-1186-A02 clinical trials will not collect information on King's Stage directly, ALSFRS-R item responses and patients' survival will be mapped to stages for every ALSFRS collected visit using the above published algorithm and patient-level data. Patients with baseline ALSFRS-R assessments that will not meet criteria for lower limb, upper limb, or bulbar involvement, and that also will not have evidence of Stage 4A or Stage 4B, will be designated "Stage 0", as their assessments could not be mapped to the King's ALS Clinical Staging System. For the King's stage derivation, the available ALSFRS-R data at each analysis visit will be used in the subjects who was not dead. If the subject was reported as a death from the last observation visit to last day of the nearest analysis visit window, King's stage from the analysis visit is Stage 5. If patients who was not death will have missing ALSFRS-R assessment at each visit, the last observation will be carried forward for the last King's stage value; In the vast majority of circumstances patients will either remain in the same clinical stage from one assessment to the next or they will experience a decline in stage. In those relatively rare instances, in which patients will be found to improve from one assessment to the next, the value from their immediately prior assessment will be used rather than the actual observed value, because the improvement will be considered to be temporary or spurious.

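### A dated tracheostomy or permanent ventilation does not move a living subject to King's Stage 4B when no usable ALSFRS-R follows it; the earlier stage is carried forward

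*SAP*

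**What the plan says.** **How stage is derived (SAP 8.4.2.8 and Table 4).**
- Source data: "ALSFRS-R item responses and patients' survival will be mapped to stages for every ALSFRS collected visit".
- Stage 4A: "Stage 4A is defined solely by impairment of swallowing sufficient to require gastrostomy". The operational rule is "If Q5B is answered, rather than Q5A".
- Stage 4B means respiratory involvement severe enough to need ventilatory support. The operational rule is "Score of 0 on Q10 or score ≤ 3 on Q12".
- Missing scores: "If patients who was not death will have missing ALSFRS-R assessment at each visit, the last observation will be carried forward". A reported death gives Stage 5. An apparent improvement is replaced by the previous stage.

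**What data may be used and how it is analysed.** SAP 9.2.1.5 limits the other secondary analyses to data up to early discontinuation and makes one exception for King's stage, which is death. SAP 9.2.1.5.7 specifies a shift table, the proportions with any decline and with a decline of two or more stages by Week 48, and the time to each. In the time-to-event analysis, dropouts without an event are censored at their first missing assessment.

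**What else is recorded.**
- On death, tracheostomy and permanent ventilation, SAP 8.4.2.4 says "If any of the events are present, the following will be recorded in the eCRF", and the event date is among the items. Protocol 12.2.4 agrees.
- Protocol 14.3, on a subject who has changed dosing route: "switched from oral to PEG/RIG tube dosing along with the switch date must be recorded in the eCRF".
- Protocol 9.6 makes tracheostomy a reason for withdrawal, and likewise a subject who "requires permanent assisted mechanical ventilation". It then requires telephone follow-up at Weeks 24, 36 and 48. Table 1 ties those calls to the three events and lists no ALSFRS-R for them.

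**The concern.** Permanent ventilation meets the SAP's own meaning of Stage 4B, and 8.4.2.8 names need for tracheostomy among the features that the staging system covers. Yet neither record enters the derivation. If no usable ALSFRS-R follows the event, a subject whose ventilation is documented in the eCRF keeps, for example, Stage 2 or 3 through Week 48. This differs from ordinary dropout, where later progression is unknown: here the stage is known and not used. The same subject would count as an event in the third key secondary endpoint (SAP 9.2.1.4.3), which includes events regardless of early discontinuation. At stake is misclassification of severe outcomes in one other secondary endpoint.

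**Working it through.** The documents give no sample size, power or event count for King's stage, so there is no figure to reproduce. The check applies the written rules to hypothetical subjects.

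**1. Table 4 plus the death, carry-forward and no-improvement rules.** Take a subject at Stage 2 from baseline to Week 24: upper and lower limb involved, items 10 and 12 both scored 4, item 5a answered.

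| Case | After Week 24 | Stage at Weeks 36 and 48 |
|---|---|---|
| A | Tracheostomy, no later ALSFRS-R | 2 and 2 |
| B | Tracheostomy, early-termination score with item 12 = 0, assigned to Week 36 | 4B and 4B |
| C | As A, but item 12 = 2 already at Week 24 | 4B and 4B |
| D | Death | 5 and 5 |

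Case A has neither any decline nor a decline of two or more stages, although both occurred. Case C loses nothing, because any BiPAP use gives item 12 ≤ 3 and therefore 4B.

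**2. Does the early-termination visit turn case A into case B?** Not reliably, for three reasons.
- Protocol 9.6 and 10.1.4 ask sites to try to complete the early-termination assessments. That is an aim, not a guarantee.
- SAP 8.5 assigns an early-termination result to the closest scheduled visit, and only if that visit has no data. Suppose Week 24 is done on Day 169, and tracheostomy and early termination both fall on Day 190. The distance to Week 24 is 190 − 169 = 21 days and to Week 36 is 253 − 190 = 63 days. Week 24 is closest and already filled, so on the plain reading of 8.5 the new score is unused and Stage 2 is carried forward.
- A subject who withdraws for another reason and has a tracheostomy or ventilation reported at a later call has no ALSFRS-R after the event, even if the early-termination visit was complete.

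**3. How wide is the gap in 8.5?** Assume every scheduled visit falls on its nominal day. From the Table 5 windows, an early-termination score is then unused on Days 30–42 (13), 58–71 (14), 86–127 (42), 170–211 (42) and 254–294 (41). The total is 13 + 14 + 42 + 42 + 41 = 152 of the 336 days from Day 2 to Day 337, and 152/336 = 45%. This is a share of calendar days, not of subjects. It shows only that the situation is not a rare corner.

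**4. Where it shows.** Carry-forward acts on the shift table and, on the plain reading, on the Week 48 proportions. In the time-to-decline analysis case A is censored at the missing Week 36 assessment (nominal Day 253), so the recorded event is again uncounted.

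**5. Unit of effect.** One affected subject changes a planned arm's proportion by 1/190 = 0.5 percentage points. The documents give no count by which to multiply this.

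**The case against.** The strongest reply is that this is the declared endpoint. Protocol 7.2.3 and 12.2.6 and SAP 3.3.3 all define the stage from ALSFRS-R and death, using a published item mapping, and SAP 9.2.1.5 states the limit at early discontinuation openly. That much stands: a reader might infer that the SAP contradicts itself, and it does not. But a declared definition does not make the carried-forward stage right. Item 12 scores invasive ventilation by intubation or tracheostomy as 0 and day-and-night BiPAP as 1. An answered item would therefore give the same 4B that the event record implies.

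Second, withdrawal triggers an early-termination visit with ALSFRS-R, within 4 days according to SAP 4.1. When that visit happens and its score is used, the gap closes. The working shows why neither is assured. One could also read 8.4.2.8 as carrying forward a stage taken from an unassigned early-termination score, but the text does not say so.

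Third, many such subjects may already be at 4B through BiPAP, may die later and become Stage 5, or may already have an any-decline event. This stands and limits the size.

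Fourth, the PEG/RIG part is weak. The date is that of a drug-route switch. Switchers stay on study and can answer item 5b at the next clinic visit, and the follow-up calls are not specified for gastrostomy. A reader might also object that an on-study gastrostomy is dated late, at the next ALSFRS-R visit. That is ordinary visit-based staging and no defect.

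Last, the events are not lost to the trial, because they are analysed in the third key secondary endpoint.

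**Conclusion.** The concern holds as a limited misclassification. A living subject with a dated tracheostomy or permanent ventilation and no usable later ALSFRS-R is shown at a milder King's stage, or is censored in the time-to-decline analysis. The number is unknown and probably small.

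Two stronger readings are tempting and unsupported. One would multiply the sizing section's implied events by an assumed non-fatal share and an assumed rate of missing ALSFRS-R, and quote a loss in percentage points. The documents give neither rate, and the product would still have to exclude subjects already at 4B, those who later die and, for any decline, those who had already declined. The other says that the arm comparison is pulled toward no difference. That needs a true difference between arms and similar loss rates in both, and neither is established.

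King's stage is an other secondary endpoint outside the fixed testing sequence in SAP 7.3, so no confirmatory conclusion depends on it. This is a worthwhile tidy-up, not a serious flaw. It rests on reading 8.4.2.8 and 8.5 as written and on some early-termination scores being absent or unassigned.

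**What to change.** 1. In SAP 8.4.2.8 state that a recorded tracheostomy or permanent assisted ventilation (≥ 23 hours/day) sets Stage 4B from the event date, and that a recorded PEG/RIG switch with no later ALSFRS-R sets at least Stage 4A. Both take precedence over carry-forward and over censoring at the first missing assessment in 9.2.1.5.7.
2. Amend the sentence in SAP 9.2.1.5 that excepts only death after early discontinuation so that it also covers these events. Otherwise the new rule conflicts with it.
3. Say which imputation applies to a partial PEG/RIG switch date. SAP 8.4.1.5 uses the first of the month and 8.4.3.1 uses the 15th.
4. Do not re-date an on-study gastrostomy when ALSFRS-R is available at the next visit.
5. Keep the derivation from ALSFRS-R and death alone as a sensitivity analysis.

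The cost is SAP wording and a merge of data already collected. The small downside is that the stage would no longer come from ALSFRS-R and death alone, which item 5 covers.

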8.4.3. Safety Measures

8.4.3.1. Adverse Events

An AE is any untoward medical occurrence in a subject or clinical investigation subject administered a pharmaceutical product that does not necessarily have a causal relationship with this IMP. An AE can therefore be any unfavorable and unintended sign (including an abnormal laboratory finding, for example), symptom, or disease temporally associated with the use of an IMP, whether or not considered related to the IMP.

Adverse events will be coded according to the MedDRA version 23.0

- Adverse Events will be classified for Treatment Emergent AEs (TEAEs) if at least one of the following conditions is met:
 - An event newly starts at Day 1 after administration of the first dose of study drug,
 - An AE documented during the pre-dose period increases in severity following dosing.
- **Handling Partial Dates:**
Events with a missing start time, but with a start date equal to the date of first dose of study treatment after baseline will be considered treatment-emergent.

If the AE start date is incomplete, it will be imputed as follows for the purpose of determining TEAE:

- If the start date is completely missing, the start date will be equal to the date of the first dose date of study drug. However, if the stop date is not missing and is before the date of the first dose of study drug, then the stop date will be used instead and the AE will not be considered as TEAE.
- If the start day is missing, but the month and year are not missing and are equal to the month and year of the first study dose, then this event will be considered as TEAE.
- If the start day and month are missing, then the first day of the first month (January) will be used.
- If an AE stop date is incomplete, it will be imputed as follows for the purpose of determining AE duration:
 - If the AE stop date is completely missing, then the stop date will be equal to the subject's last observed date.
 - If the Stop day is missing, but the month and year are not missing and are equal to the month and year of the last observed date, then stop date will be equal to last observed date.

- If the start day and month are missing, then the 31st of the last month (December) will be used.
- Adverse Events will be classified for Adverse Drug Reactions if an AE is evaluated as having causally related to the investigational product with “a reasonable possibility”

Serious Adverse Events

A serious Adverse Event (SAE) is defined as any untoward medical occurrence that at any dose:

- Results in death;
- Is life-threatening;
- Requires hospitalization or prolongation of existing hospitalization;
- Results in persistent or significant disability or incapacity;
- Is a congenital anomaly or birth defect;
- Is an important medical event.

All SAEs occurring from the time written ICF is obtained from a subject until the end of the Safety Follow-up period or the withdrawal of the subject from the study must be reported to the Sponsor/CRO. All SAEs and AESI must also be entered in the AE section of the eCRF within 24 hours.

Duration of Adverse Events

Duration of the AE and time to the AE occurrence from start of study drug will be calculated and presented in days

- Duration = AE stop date – AE start date + 1
- Time to AE occurrence = AE start date – The first administration date of study drug + 1.

Definition of Oral subgroup and PEG subgroup

The subjects start with oral administration or PEG administration. The former can switch from oral administration to PEG/RIG dosing based on the patient’s disease progresses. Therefore, if the subject started with PEG/RIG or switched from oral dosing to receiving study medication through PEG/RIG, then the subjects will be classified to PEG subgroup. Otherwise, the subjects will be classified as Oral subgroup.

Definition of TEAE under Oral dosing and PEG dosing

If the subject have the date of switch to PEG/RIG dosing or the subject start with PEG/RIG administration, TEAEs after the switched date or the first dose date will be defined as TEAEs

under PEG dosing. Otherwise TEAEs will be defined as TEAEs under Oral dosing.

- If an switch date is incomplete, it will be imputed as follows for the purpose of determining PEG duration:
 - If the switch day is missing, but the month and year are not missing, then the 15th will be used.

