#### 15 ADVERSE EVENT MANAGEMENT

All AEs and SAEs will be recorded in the source documents. All AEs and SAEs that occur from the time written ICF is obtained until the end of the Safety Follow-up Period will be recorded in the eCRF. Even if an AE is assessed by the Investigator as not related to IMP, its occurrence must be recorded in the source documents and eCRF. AEs will be classified as 'screening' if they occur before the administration of IMP. AEs will be classified as 'treatment-emergent' if they arise following the administration of IMP or if a pre-dose AE increases in severity following dosing.

At each study visit, after the subject has had an opportunity to spontaneously mention any problems, the Investigator should inquire about the occurrence of AEs. The questioning should be open-ended and non-leading.

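### An adverse event with its start day missing in the month of first dose is always a TEAE, even when its recorded stop date is before first dose

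*SAP*

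**What the plan says.** SAP 8.4.3.1 (Adverse Events) gives two ways to be a TEAE:

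- "An event newly starts at Day 1 after administration of the first dose of study drug"; or
- "An AE documented during the pre-dose period increases in severity following dosing".

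Under Handling Partial Dates it adds rules for incomplete start dates and states their purpose: "If the AE start date is incomplete, it will be imputed as follows for the purpose of determining TEAE". There are three patterns.

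1. **Start date completely missing.** The first-dose date is used, except for an event with a recorded stop earlier than first dose, for which the rule reads: "then the stop date will be used instead and the AE will not be considered as TEAE".
2. **Day missing, month and year known and the same as for first dose.** The event is a TEAE: "equal to the month and year of the first study dose, then this event will be considered as TEAE". No exception is attached.
3. **Day and month missing.** 1 January is used.

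Protocol section 15 requires eCRF recording of "All AEs and SAEs that occur from the time written ICF is obtained until the end of the Safety Follow-up Period", so collection begins well before dosing. It also says: "AEs will be classified as 'screening' if they occur before the administration of IMP".

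**The concern.** Calling an event treatment-emergent when its timing is unclear is a normal, cautious convention. That reasoning does not apply when a recorded stop date shows that the event was over before the first dose. The SAP accepts this in pattern 1. It also does so for medications in 8.4.1.4, where a stop date before first dosing makes the medication prior. Pattern 2 leaves the check out.

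An event that the definition and the protocol both treat as pre-dose would therefore be counted as treatment-emergent whenever its start is recorded to the month only. At stake is the accuracy of the TEAE counts and proportions in SAP 9.3.1.

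**Working it through.** No power, alpha or event-count figure is involved, so the check is to apply the rules to one record and compare the results.

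**Assumed record (illustrative dates, not from the documents).** First dose 20 March; adverse event stopped 10 March of the same year. The event ended 20 − 10 = 10 days before first dose.

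| What is recorded for the start | Rule that applies (SAP 8.4.3.1) | TEAE? |
|---|---|---|
| Full date, e.g. 5 March | General definition: not new after first dose, and a resolved event cannot worsen after dosing | No |
| March, day missing | Pattern 2: same month and year as first dose, stop date not consulted | **Yes** |
| Nothing | Pattern 1: stop date is before first dose | No |

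The same event changes class only at the middle level of information. Knowing the month, which is more than pattern 1 needs, turns a correct exclusion into an inclusion.

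**Does any other text supply the missing check?**

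- The later bullets in 8.4.3.1 on incomplete stop dates serve AE duration, not TEAE status.
- The protocol has no partial-date rule for adverse events.
- SAP section 11 (changes from the protocol) does not mention the point.
- SAP section 2 gives SAP analysis details precedence over the protocol's statistical text, so pattern 2 is the operative instruction.

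**Which records are exposed?** Screening takes place 8 weeks ± 7 days before Day 1 (Protocol 10.1.1), that is 56 ± 7, or 49 to 63 days. Pattern 2 reaches only the part of the first-dose calendar month before Day 1: 0 days if first dose is on the 1st, up to 30 days if it is on the 31st. Within that window, a record is affected only if the start day is missing and a stop date before first dose is recorded.

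**With the pattern 1 check applied to pattern 2,** the middle row becomes No and all three rows agree.

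**The case against.** The strongest reply is that the intent is plain and the case rare. The definition and the neighbouring rule show that the authors meant a stop date before first dose to exclude an event. Several data-handling steps reduce the chance of such a record:

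- Protocol 15.6 asks for onset and resolution dates and times, and sends conditions present before first dose to medical history unless they worsen.
- Protocol 16.1 requires missing data to be explained and discrepancies to be clarified.
- Table 1 includes adverse-event review at the baseline visit.

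Entry to the narrower tables is less likely still. An event that ended before any dose would hardly be judged possibly drug-related under Protocol 15.4. Serious events are reported within 24 hours of awareness (Protocol 15.7), so their dates are the least likely to be partial.

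All of this bears on frequency, and it stands. It does not change what the rule does to a record that meets its conditions. Events are still collected from consent, and a programmer following the SAP literally would flag such a record as a TEAE.

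Two stronger readings are tempting, and the documents support neither.

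- A reader might infer that these events receive an onset at or before Day 1, or an impossible negative duration. Pattern 2 assigns a status and no date, so onset for these records is simply unspecified.
- A reader might estimate that about half of the day-missing events in the first-dose month are misclassified. That needs dosing and onset spread evenly over the month, which the documents do not state. It also counts events whose timing really is unknown, for which TEAE status is a reasonable cautious choice. The defect covers only those with a recorded earlier stop date.

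**Conclusion.** The rule is wrong as written. It gives a result that contradicts the TEAE definition in the same section, the adjacent rule for a completely missing start date, and the screening class in Protocol section 15.

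The consequence is conditional: any record that meets all the conditions would be wrongly counted in the TEAE tables. The documents neither show that such records exist nor give a number, which is likely to be small.

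The TEAE summaries are descriptive. An event that began and ended before first dose cannot result from the assigned regimen, so randomization should leave the over-count similar in both arms. A between-arm safety bias is therefore not expected. The CAFS primary analysis, the key secondary endpoints and type I error control are unaffected. This is a minor correction.

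**What to change.** Add one sentence to the partial-date rules in SAP 8.4.3.1:

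> *If the stop date is known and is before the date of first dose, the AE is not a TEAE, whatever part of the start date is missing.*

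This extends the existing pattern 1 exception to every partial start date. Events with no stop date, or with one on or after first dose, keep their present classification.

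The cost is one sentence and the matching line in the TEAE derivation. It needs no new data and does not depend on treatment assignment. It belongs in the SAP before database lock. If lock has passed, SAP section 2 already provides for deviations from the planned analysis to be described and justified in the CSR.
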